6.1.6 Eligibility Criteria and Disease Severity

Patidegib topical gel is being evaluated in subjects with Gorlin Syndrome. Gorlin Syndrome is typically diagnosed clinically, based on the major and minor diagnostic criteria which are reflected in the inclusion criteria⁶.

The protocol requires that the subject must have had at least 10 (with at least 3 on the face) clinically typical BCCs present within 24 months prior to Randomization (Baseline/Day 1). This is to ensure that subjects with moderate to severe Gorlin Syndrome who are most likely to benefit from treatment are enrolled.

Additionally the subject must have at least 2 BCCs with longest diameter <5 mm present on the face prior to Randomization (Baseline/Day 1). This increases the possibility for developing a nSEB during the study.

6.2 Dose Rationale

The PK data from the UK Phase 2 Proof-of-Concept (Pelle-926-201) study showed 1/6 subjects on Patidegib Topical Gel, 4% had a detectable patidegib concentration in plasma at Week 14 ([REDACTED]) and 1/6 subjects had a detectable concentration at Week 26 ([REDACTED]). No

subjects on Patidegib Topical Gel, 2% had detectable concentrations (Patidegib Topical Gel IB). The tumors treated with Patidegib Topical Gel, 2% had at least as much efficacy as the Patidegib Topical Gel, 4%. The Patidegib Topical Gel, 4% group had treatment-related application site AEs (e.g., rash, dermatitis, pain, facial alopecia) that were mild-moderate in 4/6 subjects. In contrast, no treatment related AEs were seen in the Patidegib Topical Gel, 2% group (data on file, clinical study report [CSR]).

7 SELECTION AND WITHDRAWAL OF SUBJECTS

7.1 Inclusion/Exclusion Criteria

7.1.1 Subject Inclusion Criteria

Subjects meeting all of the following criteria will be eligible for study entry.

1. The subject must be at least 18 years old at the Screening Visit.
2. The subject must provide written informed consent prior to any study procedures.
3. The subject must meet diagnostic criteria for the basal cell nevus (Gorlin) syndrome including major criterion #3a plus 1 additional major criterion or plus 2 additional minor criteria listed below.

Major criteria:

- a. >2 histologically confirmed BCCs or 1 for subjects under age 20.
- b. Odontogenic keratocysts of the jaw confirmed histologically.
- c. ≥ 3 palmar and/or plantar pits seen at the Screening Visit.
- d. Bilamellar calcification of the falx cerebri present at less than 20 years old.
- e. Fused, bifid, or markedly splayed ribs.
- f. First degree relative with Gorlin Syndrome.
- g. PTCH1 mutation predicted to be of functional significance in normal tissue.

Minor criteria:

- a. Macrocephaly.
- b. Congenital malformations including frontal bossing, cleft lip or palate, “coarse face”, moderate to severe hypertelorism.
- c. Skeletal abnormalities detectable clinically: Sprengel deformity, marked pectus deformity, or marked finger syndactyly.
- d. Skeletal abnormalities detectable radiographically: bridging of the sella turcica; vertebral abnormalities such as hemivertebrae, fusion or elongation of the vertebral bodies; modeling defects of the hands and feet; flame shaped lucencies of the hands or feet.
- e. Ovarian fibroma.
- f. Medulloblastoma

(modification of criteria of V Kimonis et al Am J Med Genet 69: 299-308, 1997¹¹)

4. The subject must have had at least 10 (with at least 3 on the face) clinically typical BCCs present within 24 months prior to Randomization (Baseline/Day 1). Additionally, the subject must have at least 2 BCCs with longest diameter < 5 mm present on the face prior to Randomization (Baseline/Day 1).
5. The subject must be willing to have blood collected to measure circulating drug levels.
6. The subject must be willing to abstain from application of a non-study topical medication (prescription or over the counter) to facial skin for the duration of the trial except as prescribed by the Investigator. Moisturizers and emollients are allowed. Subjects will be encouraged to use their preferred sunscreen with a sunscreen protection factor (SPF) of at least 30 daily on all exposed skin sites.

7. If the subject is a woman of child bearing potential (WOCBP), she must be willing to use complete abstinence from sexual intercourse and/or she and her partner must be willing to use at least 2 highly-effective forms of birth control starting prior to Baseline, through the duration of the study, and for 12 months after last application of IP (Section 8.1).
8. If the subject is a male with a female sex partner who is a WOCBP, the subject must be willing to use condoms, even after a vasectomy, starting prior to Baseline, through the duration of the study, and for at least 8 months after the last application of IP.
9. The subject is willing for all facial BCCs to be evaluated and treatment recommendations made only by the Investigator.
10. The subject is willing to forego treatment of facial BCCs with anything other than the study IP except when the Investigator believes that delay of treatment of a facial BCC potentially might compromise the health of the subject. During the trial the only allowed form of treatment is surgical. Non-facial BCCs may be removed at the discretion of the Investigator or Primary Skin Care Physician (PSCP).

7.1.2 Subject Exclusion Criteria

Subjects meeting any of the following criteria will be excluded from the study.

1. The subject has previously participated in a clinical trial evaluating patidegib topical gel.
2. The subject has used topical treatment to the face or systemic therapies that might interfere with the evaluation of the study IP. Among these are use of the following:
[REDACTED]
c. [REDACTED]
[REDACTED]
[REDACTED]
[REDACTED]

3. The subject is known to have a hypersensitivity to any of the ingredients in the study medication formulation.
4. The subject is unable or unwilling to make a good faith effort to return to the study site for all study visits and tests.
5. The subject has uncontrolled systemic disease.
6. The subject has been treated for invasive cancer within the past 5 years excluding non-melanoma skin cancer, Stage I cervical cancer, ductal carcinoma in situ of the breast, or chronic lymphocytic leukemia (CLL) Stage 0.
7. The subject has current, recent (within five half lives of the experimental drug or if half life not known, within the past 6 months prior to the Screening Visit), or planned participation in an experimental drug study while enrolled in this study.
8. The subject is a WOCBP who is unwilling or unable to comply with pregnancy prevention measures.
9. The subject is pregnant or breastfeeding.

10. The subject has any condition or situation which, in the Investigator's opinion, may put the subject at significant risk, could confound the study results, or could interfere significantly with the subject's participation in the study. This may include a history of other skin conditions (e.g., severe facial eczema) or diseases, metabolic dysfunction, physical examination (PE) findings, or clinical laboratory findings giving reasonable suspicion of a disease or condition that contraindicates use of an investigational drug or that might affect interpretation of the results of the study or render the subject at high risk from treatment complications.

7.2 Concomitant Medications and Treatments

All medications listed as exclusion criteria cannot be taken concomitantly during the study.

During the study, subjects will be allowed to use moisturizers and emollients and will be encouraged to use sunscreen of at least 30 SPF at least once daily on all exposed skin sites. Subjects must wait 30 minutes after IP application before applying any moisturizer, emollient, or sunscreen.

Facial BCCs may be removed at the discretion of the Investigator by the Investigator or a competent physician/surgeon at any time after the Baseline Visit if the Investigator believes that continued growth of the BCC might have deleterious effects on the health of the subject. Non-facial BCCs may be removed at the discretion of the Investigator or PSCP.

7.3 Study Drug Discontinuation

The Investigator has the right to permanently discontinue IP application of a subject at any time if in their opinion the continuation of the IP is deleterious to the subject's health or discontinuation is in the subject's best interest. If the subject becomes pregnant, IP will be discontinued immediately.

If, for any reason, a subject is discontinued during the treatment period prior to Month 12/Exit Visit, evaluations should be performed at the time of early termination and the reason for termination will be recorded in the end of study source documentation. At the 30 day follow up additional information may be collected. All data gathered on the subject will be made available to PellePharm.

7.4 Subject Withdrawal Criteria

The Investigator may consider discontinuing a subject with a major protocol violation or deviation (e.g., failure to meet study enrollment criteria, use of disallowed medications). However, an excessive rate of discontinuation can render the study uninterpretable; therefore, unnecessary discontinuation of subjects should be avoided. A protocol violation or deviation does not in itself necessarily constitute grounds for removal of the subject from the trial if the subject's safety is not compromised.

A subject has the right to withdraw from the study at any time for any reason, without prejudice, and is under no obligation to disclose the reason. Once a subject has withdrawn from the study, no additional information can be collected. All data gathered on the subject prior to withdrawal from the study will be made available to PellePharm.

7.5 Study Discontinuation or Termination

The study may be discontinued by PellePharm in any of, but not limited to, the following events:

- Medical or ethical reasons affecting the continued performance of the study.
- Difficulties with subject recruitment that make it likely enrollment goals cannot be met.

8 STUDY PROCEDURES AND ASSESSMENTS

The study will be conducted as outlined in the schedule of assessments (SoA) ([Table 1](#)). All study visits will take place in person at the study site/clinic, except for the 30-day safety follow-up visit, which will be by phone call. All subject information and data obtained during the study visits will be recorded in the source documents, applicable study logs, and electronic case report forms (eCRFs), as appropriate.

Investigators (and any designee) must have appropriate, documented experience and training, or obtain approval from PellePharm based on experience (or through additional training organized and provided by PellePharm [or designee]). Sites will undergo a feasibility assessment, and a formal Pre-Trial Visit (PTV) conducted by the study Clinical Research Organization (CRO) (or designee). Sites that meet the requirements to conduct a study according to Good Clinical Practice (GCP) and applicable local and country regulatory requirements, as well as Investigator and site personnel with demonstrated experience and qualifications will be approved by PellePharm or designee to conduct the study. The CRO will continue the site activation process to assist sites to receive IRB approval and IP shipment and conduct of a Trial Initiation Visit (TIV) prior to the enrollment of subjects into the study for each site. In addition, at least one and preferably two site personnel will be trained in the image capture method by the imaging vendor as part of the site activation process. A back-up image capture site staff member should be available as needed.

At each study visit, every attempt should be made to ensure that the same Investigator assesses the same subject. PellePharm realizes that the conduct of a clinical trial involves a team of study staff who perform a variety of functions under the supervision of the PI. Tasks and responsibilities are delegated by the PI, and the PI is responsible for the conduct of the study at their site as well the training and oversite of all site personnel and other related non-site personnel. There are specific tasks that PellePharm requires be done by a licensed physician with appropriate experience. As outlined below and in the SoA ([Table 1](#)), these tasks include SEB biopsy procedure, assessment and reporting, BCC measurement and assessment, and recording application site reactions. The surgical excision of the BCC may be done by the Investigator or may be referred to a licensed physician with appropriate experience.

PellePharm also realizes that scheduling visits can be challenging and has allowed for flexibility with study visit days. It should be noted that the indicated visit day is in reference to the Baseline Visit. For example, the Month 8 visit is intended to be 8 months after the Baseline Visit. A month will be considered to have approximately 30 days.

8.1 Study Procedures

The SoA is provided in [Table 1](#). Subjects should be seen for all visits on the designated day or as close as practically possible. The Baseline Visit may take place no more than 45 days after the Screening visit. If this period exceeds 45 days, subjects will need to be re-screened.

The assessments/procedures to be performed at the different visits are elaborated here.

8.1.1 Informed Consent

All subjects must provide written informed consent before any study related procedures are performed. Each subject will receive a copy of the signed consent form. Subjects may be pre-screened (chart review, etc.) for eligibility prior to any study related procedure.

8.1.2 Inclusion and Exclusion

Following provision of informed consent from each subject, the Investigator will determine whether subjects meet the inclusion/exclusion criteria.

A WOCBP is defined as a woman who (a) has not undergone hysterectomy or bilateral oophorectomy or (b) has not been naturally post-menopausal for at least 24 consecutive months (i.e., has had no menses in the 24 preceding months).

A WOCBP may be enrolled if she agrees to complete abstinence from sexual intercourse or the couple agrees to use at least 2 forms of birth control as defined by the use of a condom with spermicide in association with one of the following: bilateral tubal ligation, combined oral contraceptives (estrogens and progesterone), or implanted or injectable contraceptives with a stable dose for at least 1 month prior to the Baseline Visit, or hormonal intra-uterine device (IUD) inserted at least 1 month prior to the Baseline Visit.

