8.2.3 Quality of Life Assessments

Patient reported outcome (PRO) or electronic PRO (ePRO) will be collected as outlined in

[Table 1.](#) [REDACTED]

[Table 1](#) provides the SoA for the study.

Table 1: Schedule of Assessments

Procedure	Pre-treatment	Treatment												F-Up 30 Days ^b	
	Screening ^a (-45 davs)	Baseline ^a (Day 1)	Mo 1	Mo 2	Mo 3	Mo 4	Mo 5	Mo 6	Mo 7	Mo 8	Mo 9	Mo 10	Mo 11	Mo 12	
Visit	1	2	3	4	5	6	7	8	9	10	11	12	13	14 (Exit)	15
Informed Consent ^c	X														
Inclusion/Exclusion	X	X													
Demographics	X														
Medical history ^d	X														
Current/concomitant medications	X	X	X	X	X	X	X	X	X	X	X	X	X	X	
Physical exam (including vital signs) ^e	X	X	X	X				X			X				X
Clinical laboratories and urinalysis	X	X	X	X				X			X				X
Pregnancy test ^f	X	X	X	X	X	X	X	X	X	X	X	X	X	X	
Review of contraceptive requirements	X	X	X	X	X	X	X	X	X	X	X	X	X	X	
PK sample collection ^g		X (predose)			X			X							X
Genomic sample collection (Optional) ^h		X													
Digital imaging (unmarked)	X	X	X	X	X	X	X	X	X	X	X	X	X	X	
Digital imaging (marked) and BCC measurement	X	X			X			X				X			X
Randomization		X													
Dermal Safety and Tolerability	X	X			X			X			X				X
Adverse events ^{h,i}	X	X	X	X	X	X	X	X	X	X	X	X	X	X	X
Dispense IP		X	X	X	X	X	X	X	X	X	X	X	X	X	

^a The Baseline Visit may take place no more than 45 days after the Screening Visit. If this period exceeds 45 days, the subject will need to be re-screened.

^b The safety follow-up phone call will be conducted 30 days following the subject's Exit or Month 12 visit.

^c Before signing the informed consent, site staff will review/explain the nature of the study and subject expectations to ensure the subject meets study requirements.

^d Review of systems (including the presence or absence of hair loss and change in frequency of shaving, dysgeusia, and muscle cramps), relevant family history of Gorlin Syndrome, and medical history pertinent to eligibility criteria.

^e Physical examinations will include collection of vital signs and weight (and height at Baseline only). Additional PEs may be collected according to any signs/symptoms and/or positive findings at previous PE.

^f WOCBP only: Serum pregnancy test at Screening and Month 12/Exit Visit, and serum or urine pregnancy tests at all other visits.

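### The definition of child-bearing potential joins two negated limbs with *or* where *and* is needed, so natural menopause alone exempts no one

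*Protocol*

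**What the plan says.** The definition stands in Protocol section 8.1.2. A WOCBP is a woman who "a) has not undergone hysterectomy or bilateral oophorectomy or (b) has not been naturally post-menopausal for at least 24 consecutive months". A gloss in parentheses follows limb (b): "i.e., has had no menses in the 24 preceding months".

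Four other places apply the term:

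- **Inclusion criterion 7** (section 7.1.1) requires a WOCBP to abstain or to use two contraceptive methods, from before Baseline, throughout the study and "for 12 months after last application of IP".
- **Inclusion criterion 8** (section 7.1.1) requires a male subject whose female partner is a WOCBP to use condoms during the study and "for at least 8 months after the last application of IP".
- **Exclusion criterion 8** (section 7.1.2) bars a subject if "The subject is a WOCBP who is unwilling or unable to comply with pregnancy prevention measures".
- **Table 1, footnote f** sets the testing rule: "WOCBP only: Serum pregnancy test at Screening and Month 12/Exit Visit, and serum or urine pregnancy tests at all other visits". Section 8.3.4 repeats it.

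The abbreviation list in section 3 only spells out the acronym, and the SAP does not define the term.

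**The concern.** The two limbs describe the two usual reasons why a woman cannot conceive: surgery and natural menopause. A drafter who lists both normally means that either one takes her out of the class. Because each limb is stated as a negative and the connector is *or*, the sentence does the opposite: she must have both to be exempt. Menopause then never exempts a woman on its own, and the 24-month test matters only for women who have already had surgery.

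This is an operative eligibility rule. A sexually active post-menopausal subject caught by it must use a condom with spermicide together with a method from the list in section 8.1.2, where every option is surgical or hormonal. Otherwise she must abstain or be excluded. None of this prevents a pregnancy in a woman who cannot conceive. Such subjects are plausible: the inclusion criteria set no upper age limit, and section 6.1.2 links advanced age with more BCCs.

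The wording also allows sites to differ. A literal site burdens or excludes the woman. A site that follows the evident intent enrols her without contraception and departs from inclusion criterion 7 as written. If that departure were classed as a major eligibility deviation, she would leave the per-protocol population (SAP sections 2.3 and 3.4) and lose access to the extension study (Protocol section 6). The documents do not say whether it would be so classed.

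**Working it through.** There is no sample-size, power or alpha figure to reproduce. The check is one of logic, followed by a count from the schedule.

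**Definitions**

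- S: has had a hysterectomy or bilateral oophorectomy.
- N: has been naturally post-menopausal for at least 24 months.
- A: has had no menses for at least 24 months. N implies A.

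Both N and A are needed because limb (b) names natural menopause, while its gloss, "i.e., has had no menses in the 24 preceding months", mentions only absence of menses. Either could be taken to govern. Since N implies A, there are six possible states.

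**Rules**

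- As written: WOCBP = (not S) or (not b). The exempt group is therefore S and b.
- With *and*: WOCBP = (not S) and (not b). The exempt group is therefore S or b.

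| State | *or*, b = N | *or*, b = A | *and*, b = N | *and*, b = A |
|---|---|---|---|---|
| No surgery, N | WOCBP | WOCBP | exempt | exempt |
| No surgery, not N, A | WOCBP | WOCBP | WOCBP | exempt |
| No surgery, not A | WOCBP | WOCBP | WOCBP | WOCBP |
| Surgery, N | exempt | exempt | exempt | exempt |
| Surgery, not N, A | WOCBP | exempt | exempt | exempt |
| Surgery, not A | WOCBP | WOCBP | exempt | exempt |
| **Exempt states** | **1 of 6** | **2 of 6** | **4 of 6** | **5 of 6** |

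Three results follow.

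1. The naturally post-menopausal woman without surgery (first row) is WOCBP under both readings of the current text.
2. The surgical group is caught less fully. If the gloss governs, a woman after surgery is exempt once she has had no menses for 24 months. If natural menopause governs, she stays WOCBP.
3. Changing the connector alone leaves a gap if the gloss governs: a woman without surgery whose menses stopped for another reason (second row) becomes exempt. The meaning of limb (b) therefore has to be fixed in the same edit.

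**Burden per affected person, if the rule is applied literally and treatment is completed**

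- Pregnancy tests: the Table 1 row has marks at Screening, Baseline and Months 1 to 12, so 1 + 1 + 12 = 14. Two must be serum (Screening and Month 12); the other 14 − 2 = 12 may be urine.
- Abstinence or double contraception: 12 months on treatment + 12 months after the last application = about 24 months.
- Condoms for a male subject with such a partner: 12 + at least 8 = at least about 20 months.

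**The case against.** The best case against giving this weight is practical. The term itself means child-bearing potential, so an investigator will see that the two limbs are the two ways of lacking it and will probably apply *and*. Nothing in the documents shows a site reading it literally. The burden figures are then conditional, and the number of women affected could be zero. This stands as a limit on size. It does not remove the fault: about 50 centers are planned, section 9.5 treats any departure from the protocol as a deviation, section 14.7 says no enrollment waivers are planned, and one eligibility rule should not give two answers.

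The gloss on limb (b) can also be read as the protocol's own meaning, which exempts many surgically sterile women. That is correct on that reading. It leaves the naturally post-menopausal woman without surgery untouched, and she is the core of the point.

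Timing reduces the gain. The SAP, dated 17 June 2020, describes a laboratory change midway through the study, and the protocol's sample-size text looks back to a projection made before the study began. The trial was under way, so the eligibility benefit may be small or already past. Enrolment status is not given.

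Finally, the SAP introduction mentions country-specific amendments that are not among the documents, and consent pages were removed. A correcting definition could be there; the review can speak only for the visible text.

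**Conclusion.** The definition is wrong as written. In the visible documents, a naturally post-menopausal woman with no qualifying surgery is classed as WOCBP under any reading, and some surgically sterile women are too, depending on how limb (b) is read.

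It is a minor drafting error and it errs on the safe side: no fertile woman loses protection. The ITT primary analysis, the type I error rate, power and the treatment comparison are unaffected. What it affects is eligibility and subject burden. The per-person burden calculated above assumes literal application and completion of treatment, and the total cannot be estimated. If enrolment has closed, the remaining gain is fewer tests and less contraception, including in the 12 months after the last application. The point is still worth correcting because the rule misclassifies subjects and the correction is nearly free.

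**What to change.** In Protocol section 8.1.2, change the *or* between limbs (a) and (b) to *and*, so that either qualifying surgery or natural menopause takes a woman out of the WOCBP class. In the same edit, state that menopause must be natural for limb (b), so that 24 months without menses from another cause does not by itself exempt a woman who has had no surgery. Do not make the first change without the second.

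Have the sponsor's medical lead confirm the wording, check that any country-specific amendments agree with it, and issue a clarification to sites. Leave the contraceptive methods and durations as they are.

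The cost is one changed word and one clarifying statement in an amendment, plus the site notice. No analysis changes.
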